6.4 Safety Monitoring

Adverse events in patients receiving ultrasound contrast agents will be monitored during the entire procedure and for 30 minutes from the completion of Optison infusion. Specifically, the patient will be monitored with non-leading questions to monitor the patient for the transient side effects that are described below. Changes in liver function tests (preformed clinically prior to radioembolization and 1 month) will be recorded and compared to the control group to evaluate safety and liver toxicity.

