The primary measure of tumor response will be evaluated using mRECIST criteria as determined by Drs. [name] and [name] in consensus using the patients clinically scheduled 3-4 month contrast enhanced MRI or CT. As a secondary measure of tumor response, changes in alpha fetal protein (AFP; collected as blood samples at approximately one month post embolization as standard of care) will be recorded when clinically available. Tumoral perfusion for each imaging plane will also be calculated as the slope of contrast reperfusion based on change in signal intensity over time. Perfusion values for each plane will then be averaged over the entire mass and normalized to values immediately post treatment (day 1). Finally, each patient's progression free survival and overall survival will be monitored, although this is a tertiary outcome for this study and many patients are expected to surpass the timeline of this pilot study. Safety outcomes will be determined using changes in vital signs, observed and self-reported adverse events, and changes in liver function tests (LFTs) at approximately 1 month post-embolization when available (preformed as part of clinical standard of care). Liver function tests (LFTs) include blood tests for alanine aminotransferase, alkaline phosphatase, asparate aminotransferase, bilirubin, albumin, total protein, and prothrombin time. SPECT imaging will be evaluated for all available cases by two blinded radiologists to evaluate if the initial UTMD session skews Therasphere distribution in the liver.

The proposed agent for the current study, Optison™ is a sterile non-pyrogenic suspension of encapsulated perflutren microbubbles [Goldberg et al 2001; Miller & Nanda 2004]. The contrast agent is consists of a human serum albumin shell with perflutren core and contains 5.0 - 8.0 x 10⁸ microspheres/ ml. The microbubble agent is supplied in a standard-size 3 ml vial and is prepared by manually shaking the vial. Optison will be stored in a secure refrigerator, with only the study investigators and research personnel having access. Optison is currently only approved for use in echocardiography. The agent will be used as an off-label indication for this study, but within approved dosage recommendations.

Statistical Methodology: This project is a pilot study to determine if microbubble destruction and reperfusion can used to improve treatment response of HCC to radioembolization and predict early treatment response.

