6.5 Efficacy Assessments

The primary measure of tumor response will be evaluated using mRECIST criteria as determined by Drs. [name] and [name] in consensus using the patients clinically scheduled 3-4 month contrast enhanced MRI or CT. As a secondary measure of tumor response, changes in alpha fetal protein (AFP; collected as blood samples at 1 month as standard of care) will be recorded. Finally, each patient's progression free survival and overall survival will be monitored, although this is a tertiary outcome for this study and many patients are expected to surpass the timeline of this pilot study. Safety outcomes will be determined using changes in vital signs, observed and self-reported adverse events, and changes in liver function tests (LFTs) at 1 and month post-embolization (preformed as part of clinical standard of care). Liver function tests

(LFTs) include blood tests for alanine aminotransferase, alkaline phosphatase, asparate aminotransferase, bilirubin, albumin, total protein, and prothrombin time. SPECT imaging will be evaluated for all available cases by two blinded radiologists to evaluate if the initial UTMD session skews Therasphere distribution in the liver.

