7.2.1 Sample Size Calculation

Aim 1: Little is known about the effect of UTMD on radioembolization in humans. When comparing similar groups in our animal studies, we observed relative effect sizes of 0.4 and 0.9 for tumor growth and survival, respectively. These animal study results may not apply directly to humans, but they demonstrate that large effect sizes are plausible for this intervention in subjects with HCC tumors. Under these assumptions, we have determined that a sample size of 52 patients randomized to each group would be needed in order for a Mann-Whitney U-test to have 85% power to detect a similarly moderately large relative effect of UTMD on the mRECIST score (i.e., 0.6) with a 5% type I error rate. A similar analysis is planned to compare mRECIST evaluations between 1 month and 3-4 month MRI to determine if earlier cross-sectional imaging can be used to predict long-term treatment response. Relative effect sizes for LFT, AFP, pathology, blinded reads from SPECT, planar imaging, and time to next treatment are expected to be similarly large and will also be evaluated using appropriate non-parametric or exact tests, and are each subject to the same power considerations as for the primary endpoint. Confounding of the results will be investigated and potential confounders will be included in ordinary least squares (OLS) regression models (or quantile regression models, depending on the adequacy of the data meeting OLS modeling assumptions) of these endpoints. Aim 2: A sample size of 52 would provide a two-sided test having 5% type I error rate at least 80% power to detect a Spearman's correlation of 0.4 or greater in the population. Confounding will also be evaluated for this aim and regression analysis will be considered similarly as described for Aim 1.

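### Baseline adjustment is not pre-specified for LFT and AFP; comparing changes is valid but gives up precision that adjustment would recover at little cost

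*Combined protocol and SAP*

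**What the plan says.** **LFT.** Section 6.4 has a value before radioembolization and one at 1 month, and compares the arms on the difference: "Changes in liver function tests (preformed clinically prior to radioembolization and 1 month) will be recorded and compared to the control group". The stated purpose is to assess safety and liver toxicity.

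**AFP.** This is the secondary measure of tumour response. Section 6.5 says that "changes in alpha fetal protein (AFP; collected as blood samples at 1 month as standard of care) will be recorded". Only the 1-month sample is named, so a pre-treatment sample is implied but not scheduled. The synopsis adds that AFP changes "will be recorded when clinically available", and it likewise limits the 1-month LFTs to those available.

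**Analysis.** Section 7.2.1 lists LFT and AFP among several further endpoints that "will also be evaluated using appropriate non-parametric or exact tests" and that "are each subject to the same power considerations as for the primary endpoint". It continues that "potential confounders will be included in ordinary least squares (OLS) regression models", or in quantile regression, "depending on the adequacy of the data meeting OLS modeling assumptions) of these endpoints".

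**What is left open.** The pre-treatment value is not named as a covariate. The text does not say whether the test or the regression is the main analysis, or whether change means a difference, a ratio or a log ratio. No SD, correlation or missing rate is given for either outcome.

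**The concern.** As written, the one sure use of the pre-treatment LFT is to subtract it. Subtraction gives the baseline a fixed coefficient of 1, whereas regression estimates the coefficient from the data. When baseline and 1-month values are only loosely related, subtraction adds more noise than it removes. Below a correlation of 0.5, with equal SDs, the change is noisier than the 1-month value alone.

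The regression clause does not secure the adjustment. Confounders are to be looked for and then included. A baseline that randomisation has balanced need not be flagged as a confounder, although adjusting for it would still sharpen the comparison. Because the roles of test and model are not fixed, and section 5.4 provides for no blinding, the choice could also be made after the data are seen.

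At stake is the precision of the between-arm liver-toxicity comparison and of the secondary response measure.

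**Working it through.** **Inputs from section 7.2.1:** 52 per arm, effect 0.6, type I error 5%, power 85%, Mann-Whitney test.

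**Assumed, because the documents are silent:** rho of 0.3, 0.5 and 0.7 between baseline and 1 month; normal data with equal SDs at both times; two-sided testing; complete data. The Mann-Whitney test is given its efficiency of 0.955 relative to the t-test under normality.

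**Step 1: reproduce the stated figure.** A t-test needs n = 2 × ((1.96 + 1.036)/0.6)² = 49.9 per arm, and 49.9/0.955 = 52.2. In reverse, the effective n is 52 × 0.955 = 49.66 and power = Φ(0.6/√(2/49.66) − 1.96) = Φ(1.03) = 0.848. The plan's 85% with 52 per arm therefore reproduces as a two-sided test with 0.6 read as a standardised mean difference. One-sided testing would give 0.911.

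**Step 2: variances, relative to the variance of the 1-month value.**
- Change: 2(1 − rho)
- Baseline-adjusted: 1 − rho²
- Ratio, adjusted to change: (1 + rho)/2, that is 0.65, 0.75 and 0.85 at rho 0.3, 0.5 and 0.7

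For equal precision, analysing change needs 1/0.65, 1/0.75 and 1/0.85 times as many patients: 54%, 33% and 18% more. This step does not depend on the scale of the 0.6.

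**Step 3: power if 0.6 is in SDs of the 1-month value.** Power = Φ(0.6/(s√(2/n)) − 1.96), where s is the square root of the variance in step 2 and n is 52, or 49.66 for rank methods. For example, at rho 0.3:
- Change: s = √1.4 = 1.183, power Φ(0.567) = 0.715
- ANCOVA: s = √0.91 = 0.954, power Φ(1.247) = 0.894

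| Closed-form power | rho 0.3 | rho 0.5 | rho 0.7 |
|---|---|---|---|
| Mann-Whitney on change | 0.715 | 0.848 | 0.971 |
| Rank ANCOVA | 0.880 | 0.932 | 0.987 |
| ANCOVA | 0.894 | 0.942 | 0.990 |
| Mann-Whitney on 1-month value alone | 0.848 | 0.848 | 0.848 |

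Simulation on normal data agrees to within about a point: 71/84/98% for Mann-Whitney on change, 88/92/98% for rank ANCOVA and 89/94/99% for ANCOVA. For 85% power the rank test on change needs 74, 53 and 32 per arm, and ANCOVA needs 46, 38 and 26.

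**Step 4: power if 0.6 is in SDs of the change.** The rank test on change then has 0.848 at every rho. For ANCOVA, s = √((1 + rho)/2), which gives 0.967, 0.942 and 0.913 at rho 0.3, 0.5 and 0.7.

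**AFP.** No figure is offered. The scale of change is not stated, and power for a raw difference runs from about 30% to 100% as the assumed log-SD, correlation and common fall in both arms are varied.

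**The case against.** Four stronger readings are tempting, and the documents do not support them.

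- **The analysis is unadjusted.** It is not. Section 7.2.1 plans OLS or quantile regression for these same endpoints, with a fallback if OLS assumptions fail. What stands is narrower: the one covariate sure to be useful is not named, and the model's role is not fixed.
- **The borrowed 85% power is wrong.** That needs both rho below 0.5 and an effect of 0.6 in SDs of the 1-month value. The plan states neither. Its wording on relative effect sizes can fairly be read as relative to the endpoint as analysed, in which case step 4 applies and the rank test loses nothing against 85%. At rho 0.7 the change score beats 85% even on the less favourable scale.
- **AFP loses much of its power to a raw difference.** The plan does not commit to a raw difference, and a pre-treatment AFP is only implied. This is under-specification, not a demonstrated wrong analysis.
- **Comparing changes is biased.** Under randomisation it is valid and does not inflate type I error. The loss is one of efficiency only.

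It is also fair to object that setting a rank test against parametric ANCOVA mixes two effects. The like-for-like row is rank ANCOVA, and most of the gain remains: 88% against 71% at rho 0.3, and 92% against 84% at rho 0.5. At rho 0.7 the two are practically equal in power. Finally, all the percentages assume 52 complete patients per arm, while the synopsis records these tests only when available, so actual power may be lower for every method.

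**Conclusion.** The point holds as one of efficiency and pre-specification. Baseline adjustment is more precise than comparing changes at every rho below 1, with a variance 0.65, 0.75 or 0.85 times as large at rho 0.3, 0.5 or 0.7. On the 1-month SD scale, the gain from rank test on change to ANCOVA is about 18, 10 and 1 percentage points of power. On the change SD scale it is about 12, 9 and 6 points above 85%. The rho values, normality, equal SDs and complete data are assumptions. For AFP the same reasoning applies, but no size can be given. LFT is a safety outcome and AFP a secondary measure, so the primary mRECIST comparison and the planned 104 patients are untouched. The change is worth making because it is cheap, but it is not a condition for the trial's main result.

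**What to change.** In section 7.2.1:

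- **LFT.** Pre-specify as the main comparison, for each test, a regression of the 1-month value on arm and the pre-treatment value of the same test. Use the log scale for skewed tests, or rank ANCOVA. Report the adjusted difference or ratio with a 95% CI, and keep the rank test on change as a sensitivity analysis.
- **AFP.** Use the same model on the log scale, so that the effect reads as a ratio, for patients with a pre-treatment AFP on record. State when that sample is taken.
- **Roles.** Say that this model leads, and that any further confounder adjustment is supplementary.

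Align the references to changes in LFT and AFP in the synopsis and sections 3, 6.4 and 6.5.

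The cost is SAP wording and one model term in SAS 9.4. LFT needs no new data or patients. For AFP, it must be confirmed that a pre-treatment value is routinely available.

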6.5 Efficacy Assessments

The primary measure of tumor response will be evaluated using mRECIST criteria as determined by Drs. [name] and [name] in consensus using the patients clinically scheduled 3-4 month contrast enhanced MRI or CT. As a secondary measure of tumor response, changes in alpha fetal protein (AFP; collected as blood samples at 1 month as standard of care) will be recorded. Finally, each patient's progression free survival and overall survival will be monitored, although this is a tertiary outcome for this study and many patients are expected to surpass the timeline of this pilot study. Safety outcomes will be determined using changes in vital signs, observed and self-reported adverse events, and changes in liver function tests (LFTs) at 1 and month post-embolization (preformed as part of clinical standard of care). Liver function tests

(LFTs) include blood tests for alanine aminotransferase, alkaline phosphatase, asparate aminotransferase, bilirubin, albumin, total protein, and prothrombin time. SPECT imaging will be evaluated for all available cases by two blinded radiologists to evaluate if the initial UTMD session skews Therasphere distribution in the liver.

To answer the secondary hypothesis of whether contrast reperfusion can predict treatment outcomes earlier than conventional MRI/CT imaging at 3-4 months, changes in imaging data from the experimental group will be quantified. The contrast replenishment time intensity curve will be fit with a 2-parameter exponential recovery curve: $VI = \alpha(1 - e^{-\beta t})$, in which VI represents video intensity; α (decibels) represents the asymptotic plateau correlative of the microvessel cross-sectional area, and β (in mm/s) represents the blood velocity. The product $\alpha \times \beta$ is an estimate of perfusion or blood flow per tissue unit (approximately ml/(s mg)) [Krix et al. 2003]. Parametric images from multiple slices in the tumor will also be compiled into a parametric volume to enable visualize of perfusion throughout the mass. Regions of interest will then be selected by Drs. [name] and [name] to determine average perfusion of the mass, peripheral perfusion, and vascular heterogeneity. These values will be quantified for each time point and normalized to D-CEUS at day 1. Normalized values will be grouped based on tumoral response as complete response, partial response, stable disease, and progressive disease (based on mRECIST by 3-4 month contrast-enhanced MRI/CT) to determine if D-CEUS provides an earlier indication of treatment response. Finally, changes in perfusion during the same infusion will be quantified to determine if tumor vascularity is altered during the process of UTMD.

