3.1 Trial Duration

Individual participation for patients within the experimental arm will be limited to 3 ultrasound exams. If patients are unable to make one of the 7, or 14 day visits they will still be eligible to participate. The first CEUS exam will take place 1-6 hours post radioembolization during the patient's clinically scheduled observation period. Exams at approximately 7 and 14 days post treatment will take place during separate visits to Thomas Jefferson University. The entire ultrasound imaging protocol will require approximately 90 mins including a 30 min observation period. For patients assigned to the control arm, no additional participation will be required. Patients who receive ultrasound contrast agent will be monitored for at least 30 minutes before being discharged. The research coordinator will obtain laboratory values, imaging data, and outcomes for comparison to the experimental group (all obtained as part of the patient's clinical standard of care). Subject recruitment is expected to last 83 months (March 2017 – December 2023). Analysis and publication of results are expected to take an additional 3 months (January 2024– March 2024). Volunteer Registry Database forms will be submitted to the National Institute of Health's Office of Regulatory Compliance and Quality at the completion of the research study.

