7.2 Statistical Analyses

Qualitative findings regarding treatment response will be generated by two radiologists based on mRECIST criteria at 1 and 3-4 months post treatment (using the patient's clinically scheduled contrast-enhanced MRI or CT exams). In the event of conflicting outcome reports, outcomes will be evaluated in consensus.

All statistical analysis will be performed by [name] (SKCC Biostatistics Core and faculty member) using SAS version 9.4 (Cary, NC). Aim 1: The primary hypothesis that UTMD improves the effect of

radioembolization on tumor response in HCC patients will be tested with a non-parametric Mann-Whitney U-test of the difference in response distributions between control (radioembolization alone) and experimental group (UTMD + radioembolization), measured at 3-4 months post treatment. The outcome variable in this analysis, the mRECIST score, is treated as an ordinal variable in this analysis. **Aim 2:** To test if tumor perfusion measured by CEUS between UTMD pulses predicts HCC response to radioembolization, perfusion will be characterized in terms of contrast replenishment time intensity curves fit with a 2-parameter exponential recovery curve as described above. The relationship between the normalized profusion values from this image processing and the patients' subsequent mRECIST scores in the UTMD + radioembolization group will be evaluated with Spearman's rank order correlation.

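### Aim 2 is powered as a single 5% Spearman test, but the plan names no primary perfusion measure or visit and sets no multiplicity control

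*Combined protocol and SAP*

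**What the plan says.** Section 7.2.1 gives the Aim 2 sample size: "A sample size of 52 would provide a two-sided test having 5% type I error rate" and "at least 80% power to detect a Spearman's correlation of 0.4 or greater in the population". This describes one test on the whole experimental arm.

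Section 7.2 describes the analysis. "The relationship between the normalized profusion values from this image processing" and the patients' later "mRECIST scores in the UTMD + radioembolization group will be evaluated with Spearman's rank order correlation". The predictor is plural, and neither a measure nor a visit is singled out.

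Section 6.5 describes the image processing behind those values. Regions of interest are drawn "to determine average perfusion of the mass, peripheral perfusion, and vascular heterogeneity", and "These values will be quantified for each time point and normalized to D-CEUS at day 1". The normalised values are then grouped by mRECIST category to see whether they indicate response earlier.

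The synopsis (Trial Procedures) is narrower: plane-level perfusion is averaged across the mass and normalised to the day-1 exam, giving one summary per later exam.

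Section 3 schedules up to three contrast exams: 1–6 hours after treatment, about day 7 and about day 14. Section 3.1 adds: "If patients are unable to make one of the 7, or 14 day visits they will still be eligible to participate".

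No section gives a testing order or a multiplicity adjustment for Aim 2. Section 7.2.1 also leaves confounder-adjusted regression open for this aim.

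**The concern.** The error rate and power in 7.2.1 belong to a single predictor chosen in advance. The analysis text leaves that choice open, so several correlations could be computed and the strongest reported as though it were the planned one. The 5% would then not describe the chance of wrongly concluding that CEUS predicts response.

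The conclusion has a practical use. Section 1.2 envisages that accurate prediction would let non-responders be identified early and directed to other therapies. A false-positive finding would mislead whoever designs the next study.

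A second, smaller issue concerns the number analysed. A test at one visit uses only patients with an evaluable exam at that visit and at day 1, and 52 is the full size of the arm.

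**Working it through.** **Inputs.** From 7.2.1: n = 52, two-sided α = 0.05, Spearman correlation 0.4, power at least 80%. From 6.5: three measures. From 3 and 6.5: three exams, with values divided by day 1. The day-1 value is then constant, so two visits (days 7 and 14) are informative. Not in the documents, and therefore assumed: the correlation between predictors (0 to 0.9 shown) and, for the simulation only, the mRECIST distribution (50/30/15/5% over four categories).

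**Step 1: reproduce the stated power.** Power = Φ(atanh(0.4) × √((n−3)/v) − 1.96), with atanh(0.4) = 0.4236 and n = 52.

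- v = 1 (plain Fisher z): Φ(0.4236 × 7.000 − 1.96) = Φ(1.006) = 84.3%
- v = 1.06 (Spearman variance): Φ(0.4236 × 6.799 − 1.96) = Φ(0.920) = 82.1%
- v = 1.08 (Bonett–Wright, 1 + 0.4²/2): Φ(0.4236 × 6.736 − 1.96) = Φ(0.894) = 81.4%
- Simulation of an untied Spearman test: 84.1%

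All agree with the plan's figure for one test.

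**Step 2: count the tests.** The synopsis summary gives 1 measure × 2 visits = 2. Section 6.5 gives 3 × 2 = 6. If heterogeneity is not counted as a perfusion value, 2 × 2 = 4.

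**Step 3: family-wise error if any significant result counts.** For k independent tests it is 1 − 0.95^k:

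- k = 2: 1 − 0.9025 = 9.75%
- k = 4: 1 − 0.8145 = 18.55%
- k = 6: 1 − 0.7351 = 26.5%

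With equally correlated predictors (normal simulation, plus a Spearman simulation at n = 52 with the assumed four-category outcome):

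| Assumed predictor correlation | 2 tests | 6 tests | 6 tests, Spearman simulation |
|---|---|---|---|
| 0 | 9.8% | 26.5% | 26.9% |
| 0.5 | 9.1% | 20.8% | 21.2% |
| 0.7 | 8.3% | 16.4% | 17.3% |
| 0.8 | 7.8% | 13.9% | not run |
| 0.9 | 7.0% | 10.8% | 11.7% |

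**Step 4: the price of adjusting instead.** Bonferroni over six (α = 0.05/6 = 0.0083) leaves 58.5–62.8% power at n = 52, and 80% power would need 71–76 patients. Bonferroni over two (α = 0.025) leaves 73.0–76.6%.

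**Step 5: missed visits.** The n for 80% power in one 5% test is 3 + v × ((1.96 + 0.8416)/0.4236)² = 3 + 43.7v. Rounded up, this gives 47, 50 and 51 for v = 1, 1.06 and 1.08. The margin below 52 is therefore one to five patients. As an illustration, an assumed 44 evaluable patients would give 74–77%.

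**The case against.** The strongest reply is that the plan can be read narrowly. The synopsis defines one whole-mass summary, and 7.2 speaks of tumour perfusion. Section 6.5 says that the three measures are quantified and grouped by response, not that each gets its own Spearman test. Aim 2 is also a secondary aim of a self-described pilot, where strict family-wise control is partly a matter of preference. Much of this stands, and it rules out several stronger readings that a reader might infer:

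- **That the plan commits to at least six tests.** Six is a fair reading of 6.5 with 7.2, but two is a fair reading of the synopsis.
- **That the true false-positive rate is 17–27%.** That range needs six unadjusted tests, any one counting as success, and predictor correlations between 0 and about 0.7. The measures come from the same tumour images and share a day-1 reference, so higher correlation is plausible and the rate could be 11–14%.
- **That 7.2.1 is wrong.** It attaches 5% and 80% to a single test, and the power reproduces.
- **That the within-infusion change adds a prediction test.** Section 6.5 gives it another purpose: whether UTMD itself alters tumour vascularity.
- **That every single-visit test will have fewer than 52 patients.** Section 3.1 allows a missed visit; it gives no rate and does not say that any will occur.

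The reply does not remove the gap. Even the narrowest reading leaves two visits with neither named as primary, and the synopsis and 6.5 point to different sets of predictors.

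**Conclusion.** The point holds as a gap in pre-specification. Aim 2 is sized for one test, and the analysis text does not say which test that is. If any significant correlation counts as success, the family-wise error exceeds the nominal 5% on either reading. The upper limits, 9.75% for two tests and 26.5% for six, are the independence figures; correlation between predictors brings them down as tabulated. The size therefore rests on two things the documents do not settle: how many correlations are tested and how strongly the predictors are related. Separately, the 80% power depends on at least 47–51 of the 52 patients having an evaluable exam at the tested visit. The primary endpoint is not affected. The change is worth making because it costs almost nothing before outcomes are analysed and cannot be made credibly afterwards.

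**What to change.** In 7.2, name one primary Aim 2 predictor: the whole-mass average of α × β, normalised to day 1, at one visit (day 7 or day 14) fixed before any outcome analysis. This matches the synopsis summary, since the initial slope of α(1 − e^(−βt)) at t = 0 is αβ. Test it once by Spearman at two-sided 5%. Test the other visit only if the first is significant; this fixed sequence keeps the family-wise error at 5% without splitting α. Report peripheral perfusion and vascular heterogeneity as exploratory, with confidence intervals and no significance claim.

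In 7.2.1, state that the 80% power applies to that one test and to patients with an evaluable exam at that visit, and give the expected number of such patients.

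Averaging whichever of the two later exams a patient has would retain more patients, but the predictor would then mean different things in different patients. A single named visit is cleaner.

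The cost is a few sentences and no new data or procedures. The downside is that peripheral perfusion and heterogeneity can no longer support a significance claim, and the second visit can do so only if the first succeeds. If all six correlations are to remain confirmatory, adjust for them and restate the power (58–63% at n = 52 with Bonferroni).

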2. TRIAL OBJECTIVES

Trial Objectives: The primary objective of this trial is to:

· Characterize the ability of localized ultrasound contrast agent destruction to improve hepatocellular carcinoma (HCC) response to Y90 radioembolization.

The secondary aim of this trial is to:

• Determine if contrast-enhanced ultrasound estimated tumor perfusion can reliably predict HCC response to radioembolization 1-14 days post treatment.

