CEUS studies will only be conducted with patients assigned to the experimental group (UTMD + radioembolization). Five milliliters of activated Optison will be suspended in 50 ml of saline and infused through an angiocatheter placed in a peripheral arm vein at a rate of 120 ml/hour. This total Optison administration falls within the product insert dosage guidelines (up to 5 ml within a 10 minute period and up to 8.7 ml in any one study). After confirmation of contrast-enhancement within the mass, a series of ultrasound-triggered microbubble destruction (UTMD)-replenishment sequences will be generated to cavitate UCA within the imaging plane. The patient will be asked to temporarily halt respiration while a 4 second UTMD pulse is initiated (approximate transmit parameters of MI = 1.13 at 1.5 MHz, transmitting 2.3 µs pulses at a pulse repetition frequency of 100 Hz), followed by nonlinear imaging of contrast replenishment at lower intensity using Cadence Pulse Sequencing (MI = 0.06) for 10 seconds. Following patient respiration, this sequence will be repeated at multiple imaging planes throughout the tumor and then repeated throughout the entire tumor volume for the duration of the infusion (UTMD expected in 10-20 planes, repeated 3-4 times). In the few patients with multiple Y-90 treated tumors, the largest tumor will be selected for UTMD therapy and outcomes compared to the non-UTMD treated tumors outside the acoustic field. This sequence will be repeated at imaging planes throughout the tumor for the duration of the infusion. Following completion of the infusion, patients receiving ultrasound contrast agent will be monitored for adverse events for 30 minutes to ensure stable response.

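### The Aim 2 test uses only perfusion normalized to the day-1 exam, so it can give no result at day 1, where the objective's 1-14 day prediction window begins

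*Combined protocol and SAP*

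**What the plan says.** Section 2 asks whether CEUS-estimated perfusion "can reliably predict HCC response to radioembolization 1-14 days post treatment". CEUS is done only in the experimental group, at up to three exams. Section 3.1 states: "The first CEUS exam will take place 1-6 hours post radioembolization"; the others fall at about 7 and 14 days.

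Section 6.5 derives average perfusion, peripheral perfusion and vascular heterogeneity from the replenishment curves, with alpha x beta as the perfusion estimate. It continues: "These values will be quantified for each time point and normalized to D-CEUS at day 1". The synopsis (Trial Procedures) gives the same rule and identifies day 1 with the exam immediately after treatment. Neither place says whether normalizing means a ratio or a difference.

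Section 7.2 describes the Aim 2 quantity as "tumor perfusion measured by CEUS between UTMD pulses" and relates the normalized values to later mRECIST by Spearman's correlation. Section 7.2.1 claims at least 80% power for a correlation of 0.4 with 52 patients and names no time point.

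Within an exam, Section 6.3 expects destructive pulses in 10-20 planes, gone through 3-4 times. Section 6.5 adds that "changes in perfusion during the same infusion will be quantified to determine if tumor vascularity is altered during the process of UTMD".

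**The concern.** The objective's window opens at day 1, but the only predictor carried into the test is fixed by construction at day 1. No section relates un-normalized day-1 perfusion to mRECIST. The only pre-treatment ultrasound is without contrast (Sections 6.1 and 6.2), so there is no earlier CEUS exam to serve as the reference instead.

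The purpose of Aim 2 is earlier prediction. As written, the earliest exam never appears as a predictor in its own right. It is also the exam least exposed to missed visits: it falls within the clinical observation period, whereas Section 3.1 allows a day-7 or day-14 visit to be missed. If perfusion a few hours after treatment were informative, the planned test could overlook it.

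**Working it through.** **1. The plan's own power figure.** Inputs from Section 7.2.1: n = 52, Spearman correlation 0.4, two-sided alpha 0.05. With the Fisher z approximation, power = Phi(atanh(0.4) x sqrt((n - 3)/v) - 1.96), where atanh(0.4) = 0.4236 and v is the variance factor.

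- v = 1 (Pearson): 0.4236 x 7.000 - 1.96 = 1.006, power 84.3%.
- v = 1.06 (Fieller, for Spearman): 0.4236 x 6.799 - 1.96 = 0.920, power 82.1%.
- v = 1 + 0.4²/2 = 1.08 (Bonett-Wright, for Spearman): 0.4236 x 6.736 - 1.96 = 0.894, power 81.4%.

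All three meet the stated figure, so it reproduces.

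**2. The planned predictor at day 1.** Write P1 for a patient's day-1 perfusion. As a ratio, P1/P1 = 1 for everyone; as a difference, P1 - P1 = 0. All ranks are tied, the rank variance is zero, and Spearman's correlation is 0/0. A numerical check with 52 simulated patients returned an undefined result both ways. The 81-84% can therefore describe only the day-7 and day-14 predictors. It would describe day 1 only if the un-normalized value were used, its true correlation were 0.4 and all 52 patients had it.

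**3. How much a day-1 signal shows through the ratio (assumed data).** n = 52 and 4,000 simulated trials per setting. Log day-1 perfusion has a Spearman correlation of about 0.40 with a four-level response, and day 7 carries no independent signal.

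| Assumed day-1 to day-7 correlation | Power, raw day 1 | Power, day-7/day-1 ratio |
|---|---|---|
| 0.3 | 84.0% | 39.9% |
| 0.5 | 84.9% | 29.6% |
| 0.8 | 84.4% | 14.5% |

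The ratio retains some of a day-1 signal but is a weak substitute for testing it directly. The setting is deliberately unfavorable to the ratio, since it puts no signal in day 7.

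**4. Does averaging over passes distort the ratios?** Let the averaged value for patient i at visit v be the first-pass value times a factor c(i,v) for change during the infusion. The day-7 ratio is then multiplied by c(i,7)/c(i,1).

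- If c depends only on the patient, it cancels.
- If c depends only on the visit, every ratio is multiplied by the same constant and the ranks do not move.
- If c is a patient factor times a visit factor, the same constant results.
- Only a change that differs by both patient and visit can reorder the ratios.

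If normalizing means a difference, the same argument holds for changes that add rather than multiply.

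For scale, suppose perfusion fell 10-20% per pass (an assumption with no source in the documents). The four-pass mean would be (1 + 0.9 + 0.81 + 0.729)/4 = 0.86 to (1 + 0.8 + 0.64 + 0.512)/4 = 0.74 of the first-pass value. The three-pass mean would be 0.90 to 0.81. That is a shift of 10-26% in the raw mean, not in the ranked ratio.

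**The case against.** The strongest reply is that day 1 is the baseline by design. Section 6.5 introduces this aim in terms of changes in imaging data, and the background and rationale (Sections 1.1 and 1.2) rest on changes in perfusion and inflammation. A change score is constant at its own baseline, and that is not a defect. The 1-14 day phrase can be read as the period over which change is observed. Prediction earlier than the 3-4 month scan can be tested at day 7 or 14. This stands as a defense of the ratios, which are valid and should stay. It does not fill the gap at the first exam of the stated window.

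A second reply also stands in part. Alpha x beta is built from video intensity, and Section 6.3 allows two scanner models and three probe options. Normalizing within a patient plausibly protects against equipment differences, and a raw day-1 value loses that protection. This is a reason to call the raw analysis exploratory and report the equipment, not to leave it out.

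Two stronger readings are tempting and are not supported. A reader might infer that day 1 contributes no information; in fact it is the denominator of every later ratio. A reader might also infer that measuring the reference during UTMD biases every normalized value. The documents treat a change in vascularity during the infusion as an open question, with no size or direction, and step 4 shows that only a patient-by-visit difference would alter the ranks. First-pass curves are not free of UTMD either, since each follows a destructive pulse.

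**Conclusion.** The point holds for the planned analysis. The Spearman test can give no day-1 result whichever way normalization is done, and the stated power cannot apply there. This follows from the wording of Sections 2, 6.5 and 7.2 alone. It does not mean the objective is unanswerable at day 1: the raw values will exist and no new exam is needed. The simulated loss of power (about 84-85% down to 15-40%) rests wholly on the assumed data in step 3 and should not be read as an estimate for this trial. Since this is a secondary aim of a pilot study, the change is an inexpensive improvement rather than a correction on which the trial depends.

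**What to change.** Amend Sections 6.5, 7.2 and 7.2.1 as follows.

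- Keep the day-7/day-1 and day-14/day-1 predictors, state that normalization is a ratio, and say that the power statement refers to these predictors.
- Add un-normalized day-1 whole-mass alpha x beta as a named exploratory Aim 2 predictor of 3-4 month mRECIST by Spearman's correlation. Report it with scanner and probe, because raw video intensity may differ between them.
- State which passes enter the averaged value. As a sensitivity analysis only, repeat the ratios using first-pass curves.

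The cost is wording plus one further exploratory correlation, on a value without within-patient normalization. First-pass values average fewer curves and are noisier, which is why they should not replace the main ratios.
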